6.6 Treating the patient

6.6.1 Permitted drug dose adjustments and interruptions

Fingolimod dose adjustments are not permitted, although interruptions may be warranted according to label.

6.6.2 Rescue medication

Not applicable.

6.6.3 Recommendations on treatment of MS relapse

Following an onset of MS relapse the patient may have unscheduled visits in the investigator's discretion. Handling of MS relapses will be performed according to local practice and standard of care procedures.

A standard course of corticosteroids (methylprednisolone) on an inpatient or outpatient basis is allowed for treatment of relapses as clinically warranted and should be recorded in the CRF.

Steroid treatment should consist of 3-5 days and up to 1,000 mg methylprednisolone/day. Standard of care procedures will be followed during treatment.

Use of any oral tapering is not permitted.

The use of steroid for MS relapses therapy should be recorded on the "Prior-/concomitant medications" CRF.

Investigators should consider the added immunosuppressive effects of corticosteroid therapy and increase vigilance regarding infections during such treatment and in the weeks following administration.

Should a patient show evidence or suspicion of infection, please refer to actual Summary of product Characteristics.

In the event that steroids are administered patients should be reminded of the importance of reporting any signs or symptoms of an infection. Special consideration should be given to symptoms or signs of herpes simplex or zoster reactivation (e.g. lancinating pain, skin lesions) and appropriate antiviral therapy (e.g. acyclovir, valacyclovir) should be promptly initiated

and continued for up to 30 days after stopping high dose steroid treatment. An infectious disease specialist may be consulted to guide such therapy if needed.

Should a patient develop any neurological symptoms or signs, unexpected for MS in the opinion of the investigator or accelerated neurological deterioration, the investigator should immediately schedule an MRI according to local practice.

In case of acute optic neuritis or MS relapse the OCT assessment should be postponed for at least 30 days (at the discretion of the investigator) and the circumstance must be recorded in the corresponding CRF.

6.6.4 Study completion, post-study treatment and early study termination

The study will be considered completed for an individual patient when he/she completes visit 7.

After premature withdrawal Visit 7 should be scheduled as soon as possible.

The study can be terminated for reasons stipulated in the study contract. Should this be necessary, the patients should be contacted and scheduled for their end of study assessments as described in Section 7. Novartis will be responsible for informing IRBs and/or IECs of the early termination of the study.

7 Visit schedule and assessments

Table 7-1 lists all of the assessments and indicates with an “X” the visits when they are performed and recorded in the clinical database.

Patients who prematurely withdraw from the study for any reason, should be scheduled for a final visit, at which time all of the assessments listed for the final visit will be performed.

Patients should be seen for all visits on the designated day with an allowed visit window of +/- 14 days for visits 3 to 7.

In addition to the scheduled visits, patients may have unscheduled visits following an infection, relapse or for other reasons as indicated in the protocol. All information should be collected.

Medications used to treat MS may include glatiramer acetate (Copaxone[®]), interferon β -1a i.m. (Avonex[®]), interferon β -1a s.c. (Rebif[®]), interferon β -1b (Betaseron[®]/Betaferon[®]), natalizumab (Tysabri[®]), azathioprine, methotrexate or any other medications used as MS-disease-modifying agents. Patients are not allowed to take these medications during the study. Other medications to treat MS-related symptoms should be recorded in the Concomitant Medication CRF. MS history should be supplemented by review of the patient's medical chart and/or by documented dialog with the patient's referring physician.

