5.2 Premature patient withdrawal

Patients must be withdrawn from the study for any of the following reasons:

- Withdrawal of informed consent
- Investigator's decision (withdrawn in the best interest of the patient for any reason)
- Use of prohibited medication (see section 6.4 Prohibited Treatment)

Patients should be withdrawn at any time if the investigator concludes that it would be in the patient's best interest for any reason. Protocol violations should not lead to patient withdrawal unless they indicate a significant risk to the patient's safety.

Patients may voluntarily withdraw from the study for any reason at any time. They may be considered withdrawn if they state an intention to withdraw, or fail to return for visits, or become lost to follow up for any other reason.

If premature withdrawal occurs for any reason, the investigator must determine the primary reason for a patient's premature withdrawal from the study and record this information on the Study Completion CRF.

For patients who are lost to follow-up (i.e., those patients whose status is unclear because they fail to appear for study visits without stating an intention to withdraw), the investigator should show "due diligence" by documenting in the source documents steps taken to contact the patient, e.g., dates of telephone calls, registered letters, etc.

Patients who are prematurely withdrawn from the study will not be replaced by newly enrolled patients.

6 Treatment

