7.3 Optical coherence tomography

Optical Coherence Tomography (OCT) will be assessed for both eyes at Baseline (Visit 2), Visit 3, 4, 5, 6, and 7. Anxiety/Stress, Comfort and Satisfaction - Level (Appendix 8) will be recorded after the first scan. These assessments will be performed by trained personnel at each site. All OCT Scans will be analyzed and quality controlled by a Central Reading Center (CRC), see section 9.3. The patients identity will be masked for all information forwarded to the CRC during the study. A copy of the OCT images will be retained with the source documents at each investigative site.

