1.1 Study design

This is a multi-center, open-label study in RRMS patients treated with fingolimod. After signing the informed consent, patients will enter a Screening Phase (day -28 to day 0) before starting the study at Baseline (visit 2/day 0), followed by a 36-month longitudinal data collection phase. Visits are performed at month 3 (visit 3), month 6 (visit 4), month 12 (visit 5), month 24 (visit 6), and month 36 (visit 7). Eligibility will be determined at Screening. OCT and other assessments will be performed according to the schedule in Table 7-1 of the Clinical Study Protocol (CSP).

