2.3.1 Patient disposition

The disposition of all enrolled patients displays the number and reasons of screening failures.

The disposition of all patients in the treatment period (i.w. who received at least one dose of fingolimod) displays the number and reasons for premature discontinuation from the study.

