2.5.2 Statistical hypothesis, model, and method of analysis

No hypothesis is to be tested.

Descriptive pairwise comparisons are performed using a paired t-test in case of normality, In case of non-normality a Wilcoxon signed-rank test is applied instead. No adjustment for multiple comparisons are made. For each parameter the normality distribution is graphically proved for the change from BL to M36. Differences as well as pre-post ratios are displayed. When non-normality is detected for the change to M36 the changes to M12 respectively M36 are analysed also non-parametrically.

The primary efficacy variable is presented graphically by standard boxplots for each time point. Sample statistics are presented for each time point and changes (differences as well as ratios) to each time point.

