2.5.3 Handling of missing values/censoring/discontinuations

Missing values are replaced by the last available value. Post-baseline values are carried forward but no baseline values.

An analysis without replacing the missing data is performed as sensitivity analysis.

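### An OCT scan from an early-withdrawal Visit 7 counts as an observed month-36 value in the FAS, so the no-replacement analysis says little about truncated follow-up

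*Protocol*

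**What the plan says.** **The withdrawal visit.** Protocol 6.6.4: "After premature withdrawal Visit 7 should be scheduled as soon as possible". Protocol section 7 adds that the withdrawn patient has every final-visit assessment. Protocol 7.3 makes OCT one of them: it "will be assessed for both eyes at Baseline (Visit 2), Visit 3, 4, 5, 6, and 7".

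**The label month 36.** SAP 1.1 ends its visit list with "month 24 (visit 6), and month 36 (visit 7"). SAP 2.8.4.2 uses the same pairing, V7/M36.

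**Replacement.** The SAP's definition of the last value until a given visit is indexed by visit and replaces only missing or invalid data. For the primary endpoint, SAP 2.5.3 adds: "An analysis without replacing the missing data is performed as sensitivity analysis". SAP 2.5.2 states: "Sample statistics are presented for each time point and changes (differences as well as ratios) to each time point".

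**Timing.** The only visible rule on the timing of Visit 7 is deviation O3 in SAP 5.4, Table 1: a Visit 7 no more than 1035 days after baseline excludes the patient from the per-protocol analysis. Table 2 lists O3 for the PPS but not for the FAS.

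**The withdrawal record.** Under Protocol 5.2 the investigator must determine the primary reason for withdrawal and "record this information on the Study Completion CRF". The disposition table in SAP 2.3.1 "displays the number and reasons for premature discontinuation from the study".

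**The concern.** One visit number serves two purposes. For a completer, Visit 7 is the month-36 scan. For a withdrawn patient who attends, it is a scan at whatever month the patient left. The visible SAP has no rule that takes the second kind out of month 36 in the FAS.

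The no-replacement analysis is the planned FAS check on LOCF for the primary endpoint. A reader will expect it to show what happens when patients without 36 months of follow-up supply no month-36 value. As written, it keeps the early scan of every withdrawn patient who attended Visit 7, and LOCF uses that same scan. Agreement between the two could then be taken as evidence that truncated follow-up does not matter. The month-36 sample statistics would likewise mix follow-up lengths under one label.

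**Working it through.** The plan states no dropout rate, attendance rate, slope or SD, so there is no figure of its own to reproduce. The calculation below is illustrative.

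**Inputs from the documents.** Scans at months 3, 6, 12, 24 and 36 (SAP 1.1); LOCF from post-baseline values only (SAP 2.5.3); O3 limit of 1035 days (SAP 5.4).

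**Assumptions.** Thinning is linear with the same slope in all patients. A share *d* withdraws, uniformly over 36 months. A share *a* of these attends Visit 7 at withdrawal. Attendance is uncertain also because the Protocol glossary says no further assessments are planned at withdrawal, while 6.6.4 and section 7 ask for the final visit. Ranges are therefore shown.

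**O3 limit.** 36 × 365.25/12 = 1096 days, and 1035 days is 34.0 months. A Visit 7 up to about two months early stays in the PPS; an earlier one leaves the PPS but remains in the FAS.

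**Mean scan time of withdrawn patients.**
- With Visit 7: 36/2 = 18 months.
- Without Visit 7: the last scheduled scan contributes (3×3 + 6×6 + 12×12 + 12×24)/36 = 13.25 months per withdrawal. A share 33/36 has a post-baseline scan and stays in the FAS.

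**Fraction of the true 36-month change recovered.**
- LOCF = [(1−d)·36 + d·(a·18 + (1−a)·13.25)] / [(1−d) + d·(a + (1−a)·33/36)] / 36
- No-replacement = [(1−d)·36 + d·a·18] / [(1−d) + d·a] / 36

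For d = 0.2 and a = 0.8:
- LOCF = (28.8 + 3.41)/0.99667/36 = 0.898
- No-replacement = (28.8 + 2.88)/0.96/36 = 0.917
- Withdrawal scans set to missing (completers) = 1.000

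| Dropout | Attendance | LOCF | No-replacement |
|---|---|---|---|
| 10% | 80% | 0.949 | 0.959 |
| 20% | 80% | 0.898 | 0.917 |
| 30% | 80% | 0.846 | 0.872 |
| 20% | 50% | 0.894 | 0.944 |
| 20% | 100% | 0.900 | 0.900 |

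A simulation of 4,000 trials of 100 patients at −1.0 micron per year (true change −3.0), with 20% dropout, agrees. At full attendance both analyses gave −2.70; at 50% attendance they gave −2.68 and −2.83.

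**Month-36 summaries.** Per 100 patients at 20% and 80%, 80 completers and 16 withdrawn patients have a Visit 7 scan. So 16/96 = 17% of the observed month-36 values are withdrawal scans, and mean follow-up is (80×36 + 16×18)/96 = 33.0 months.

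**PPS, applying O3 only.** A share (36 − 34.004)/36 = 0.0554 of attended withdrawal scans falls after day 1035, at a mean of 35.0 months. If patients with no Visit 7 stay in: (28.8 + 0.16×0.0554×35.0 + 0.04×13.25)/(0.8 + 0.0089 + 0.0367)/36 = 0.974. The share of the LOCF shortfall shown is (0.974 − 0.898)/(1 − 0.898), about 74%.

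**In microns.** Protocol section 1 speaks of a few microns. For an assumed true change of 1 to 5 microns, LOCF and no-replacement differ by 0.019 × 1 to 5 = 0.02 to 0.10 microns. LOCF and completers differ by 0.102 × 1 to 5 = 0.10 to 0.51 microns.

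**If withdrawn patients thin faster** (20% dropout, 80% attendance; completers' slope = 1):
- Twice as fast: truth 0.8 + 0.2×2 = 1.20; LOCF (28.8 + 0.4×17.05)/0.99667/36 = 0.993; no-replacement (28.8 + 0.16×36)/0.96/36 = 1.000; completers 1.000.
- Three times as fast: truth 0.8 + 0.2×3 = 1.40; no-replacement (28.8 + 0.16×54)/0.96/36 = 1.083; completers 1.000.

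**The case against.** **A rule may exist in text that could not be read.** Only the last definition of SAP 2.1 is available, and SAP 5.2 and Protocol Table 7-1 are not. Nowhere does the visible SAP say outright that a withdrawal scan is a month-36 value; this follows from visit-based definitions. The objection stands as a condition on the finding. O3 does show, however, that the SAP expects an early scan to keep the Visit 7 label.

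**The PPS already covers it.** In part. It shows most of the shortfall for the primary endpoint under the assumptions above. But O3 is one of 22 rows in Table 1, and most of the others also act on the PPS alone. A difference between FAS and PPS therefore cannot be put down to follow-up length. SAP 2.7.2 limits the secondary analyses to the FAS.

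**Withdrawn patients can be identified.** This is right. Protocol 6.6.4 also says "The study will be considered completed for an individual patient when he/she completes visit 7", and a reader might infer that a withdrawn patient who attends becomes indistinguishable from a completer. The documents do not support that: the glossary defines premature withdrawal separately, Protocol 5.2 records it and SAP 2.3.1 tabulates it. What is missing is a visible link from that record to the OCT time point.

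**Removing the scans discards data and may not help.** This stands too. Completers alone are closer to the truth only if withdrawn patients thin less than twice as fast as completers. At twice the slope the two versions are equal, and at three times the slope the scans bring the estimate nearer the truth. This limits what the revised analysis may be said to show.

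**Conclusion.** The point holds and is minor. On the visible text, early-withdrawal scans enter the no-replacement analysis and the month-36 sample statistics as observed month-36 values. For withdrawn patients with a valid Visit 7 scan, that analysis cannot differ from LOCF. The sizes above rest on assumed dropout, attendance and a common linear slope, none of which the documents give.

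Three stronger readings are not supported.
- A reader might infer that the label biases the primary estimate. The shortfall in LOCF comes from carrying short follow-up forward, which the plan does openly; relabelling the scan leaves that estimate unchanged.
- A reader might infer that the two analyses are always the same. They coincide only for withdrawn patients with a valid Visit 7 scan. Those without one are carried forward in one analysis and dropped in the other, which is why 50% attendance gives 0.894 against 0.944.
- A reader might infer that a corrected analysis would test for informative dropout. It would not, as the faster-thinning cases show.

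The study is exploratory and tests no hypothesis (SAP 2.5.2), so what is at stake is interpretation of a sensitivity analysis.

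**What to change.** State in SAP 2.5.3 that a Visit 7 scan in a patient recorded as prematurely withdrawn on the Study Completion CRF is an early-termination scan. Keep it for the LOCF value. Treat it as missing at month 36 in the no-replacement analysis and in the month-36 summaries. Report that analysis as completers only, showing the effect of truncated follow-up, and not as a check on informative dropout.

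The cost is a short SAP text and one derived flag from an item already collected. Fewer patients count as observed at month 36: 80 instead of 96 per 100 at 20% dropout and 80% attendance. At unchanged SD, the standard error of that analysis rises by √(96/80) − 1, about 10%. For dropout of 10% and 30% at the same attendance, the rise is √(98/90) − 1 = 4% and √(94/70) − 1 = 16%.

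If SAP text that could not be read here already assigns scans to month 36 by date, a cross-reference in 2.5.3 is enough.

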7.2 Ophthalmologic examination

A complete ophthalmologic examination will be performed by an ophthalmologist as described in Table 7-1. The exam will include previous eye history and any new ophthalmic symptoms, best corrected visual acuity, dilated ophthalmoscopy and optical coherence tomography (OCT) for the measurement of central foveal thickness. Substitution of OCT with fluorescein angiography will not be permitted. Details on the ophthalmologic examinations are provided in the Guidance for Ophthalmic Monitoring Appendix 7.

An ophthalmological examination is regularly recommended 3-4 months after commencing fingolimod therapy (according to local label). If patients report visual disturbances at any time while on therapy, evaluation of the fundus, including the macula, should be carried out.

7.3 Optical coherence tomography

Optical Coherence Tomography (OCT) will be assessed for both eyes at Baseline (Visit 2), Visit 3, 4, 5, 6, and 7. Anxiety/Stress, Comfort and Satisfaction - Level (Appendix 8) will be recorded after the first scan. These assessments will be performed by trained personnel at each site. All OCT Scans will be analyzed and quality controlled by a Central Reading Center (CRC), see section 9.3. The patients identity will be masked for all information forwarded to the CRC during the study. A copy of the OCT images will be retained with the source documents at each investigative site.

7.4 Treatment exposure and compliance

In order to collect information about the medications taken, the following records should be maintained for each patient participating in this study: records of medication prescribed, interruptions in fingolimod intake and intervals between visits.

Compliance will be assessed by the investigator and/or study personnel at each visit using information provided by the patient.

7.6 Safety

- Physical/neurological examination
- Vital signs
- Laboratory evaluation

7.6.1 Physical examination

A complete physical examination will be performed at visits as described in [Table 7-1](#) and will include an assessment of skin, head and neck, lymph nodes, breast, heart, lungs, abdomen, back and comments on general appearance. Initial neurological examination will be a part of the physical examination. All significant findings that are present prior to start of the trial must be reported on the Relevant Medical History/Current Medical Conditions CRF. Significant findings made after the start of study which meet the definition of an AE must be recorded on the Adverse Event CRF.

7.6.2 Vital signs

Vital signs will be recorded as described in [Table 7-1](#). Vital signs will include sitting pulse rate, sitting systolic and diastolic blood pressure (3 measurements), oral temperature (degrees Celsius), body height (cm) and body weight (kg). Height and body weight will only be collected at Visit 2; see Appendix 3.

7.6.3 Laboratory evaluation

Routine blood samples (10 ml at each visit; also at unscheduled visits in case of an infection) will be collected at the visits described in [Table 7-1](#) and analyzed by a local laboratory.

Investigators will be asked to comment on any abnormalities on the respective lab result page, including a notation of the clinical significance of each abnormal finding in the patient's source documents. The laboratory sheets will be filed with the patient source documents. Abnormal laboratory values should not be recorded on the adverse event CRF; however, any diagnoses (or signs or symptoms if a diagnosis is not possible) associated with the abnormal findings should be recorded on the adverse event CRF.

Hematology

Hematology parameters will be collected at the visits described in [Table 7-1](#) and [Appendix 2](#) and will include: RBC count, total WBC, differential blood count (lymphocytes), platelet count, hemoglobin, and hematocrit.

Chemistry

Blood samples will be collected at the visits described in [Table 7-1](#) and [Appendix 2](#). Measurements will include the following parameters: sodium, potassium, chloride, calcium, blood urea nitrogen (BUN), random glucose, alkaline phosphatase, creatinine, Bilirubin, ALT, AST, and GGT.

Notable abnormalities are defined in the Criteria for clinically notable laboratory values and vital signs further specified in [Appendix 3](#).

Abnormal laboratory parameters, inconsistent with clinical presentation of MS or suspicious of underlying medical condition, should be repeated for accuracy.

7.6.4 Pregnancy and assessments of fertility

Serum pregnancy test will be performed for all women prior to inclusion. Additional pregnancy testing may be performed at the investigator's discretion during the trial. Patients becoming pregnant must discontinue the study.

Women of child bearing potential must use one of the below listed medically approved methods of contraception (Pearl Index <1):

Primary forms:

- hormonal contraception (combination oral contraceptives, hormonal transdermal patch, combined injected hormones, injected single hormone, implanted hormones, or hormonal vaginal ring)
- tubal sterilization
- partner's vasectomy
- intrauterine device (synthetic progestin containing IUDs, IUD copper T380)

Secondary forms: Barrier forms (always used with spermicide)

- latex condom
- diaphragm

- cervical cap

Others:

- vaginal sponge (contains spermicide)

Oral contraceptives without estrogen (e.g. "mini-pills"), nonsynthetic progesterone only IUDs, female condoms, cervical shield, periodic abstinence (e.g., calendar, ovulation, symptothermal, post-ovulation methods) and withdrawal are not acceptable methods of contraception. Reliable contraception should be maintained throughout the study and for 8 weeks after study drug discontinuation.

At the discretion of the investigator, total abstinence from sexual intercourse is acceptable in cases where the age, career, lifestyle, or sexual orientation of the patient ensures the prevention of pregnancy.

7.7 MS Relapse

A patient should report symptoms indicative of an MS relapse at a scheduled visit or any other time. Patients must be instructed to immediately contact the study site if he/she develops new, reoccurring or worsening neurological symptoms. Standard therapy with corticosteroids can be used. Following an onset of MS relapse the patient may have unscheduled visits at the discretion of the investigator. Handling of MS relapses will be performed according to local practice and standard of care procedures. Details of MS relapse handling will be recorded in the corresponding CRF.

